6.5 Final Follow-up Assessment

Final Follow-up Assessment 3, Day 56 (-6 days to +6 days) (t_{1_3})

Patients will complete pain assessment/compliance/satisfaction with treatment questionnaire.

6.6 Study Visits for Patients Returning for Additional Treatment

- Patients who do not have a reduction of symptoms after the first-line treatment may return to the participating dentist for a second-line treatment due to continued discomfort and/or dentist's recommendation if the dentist routinely utilizes a "stepped approach" to DH management. If this occurs within 8 weeks of the initial treatment, study procedures (VAS, pain intensity, clinical exam) will be repeated for each second-line and third-line treatment that is administered or prescribed.
- Recommended (by dentist) and actual (when appointment occurs) time interval(s) between treatment(s) will also be recorded. Patients will be contacted via text message system, phone or email 1-, 4- and 8-weeks post-additional treatment and will be followed until 8 weeks after the last administered DH treatment.

6.6.1 Second-Line Treatment Visit

Second-Line Treatment Visit (t_{2_0}) may occur between 1-56 days ($1 \leq t_{2_0} \leq 56$) since the baseline visit at t_{1_0} :

- Obtain patient self-reported pain assessments.
- Record results of dental examinations.
- Record treatment recommendations and treatment administered/prescribed.

Follow-up Assessment 1, Day 7 + t_{2_0} (-6 days to +6 days) (t_{2_1})

- Patients will complete pain assessment/compliance to treatment questionnaire.

Follow-up Assessment 2, Day 28 + t_{2_0} (-6 days to +6 days) (t_{2_2})

- Patients will complete pain assessment/compliance to treatment questionnaire.

Final Follow-up Assessment 3, Day 56 + t_{2_0} (-6 days to +6 days) (t_{2_3})

- Patients will complete pain assessment/compliance/satisfaction with treatment questionnaire.

6.6.2 *Third-Line Treatment Visit*

Third-Line Treatment Visit (t_{3_0}) may occur between 1-56 days ($1 \geq t_{3_0} \leq 56$) since the second-line treatment visit at t_{2_0} :

- Obtain pain assessments.
- Record results of dental examinations.
- Record treatment recommendations.

Follow-up Assessment 1, Day 7 + t_{3_0} (-6 days to +6 days) (t_{3_1})

- Patients will complete pain assessment/compliance to treatment questionnaire.

Follow-up Assessment 2, Day 28 + t_{3_0} (-6 days to +6 days) (t_{3_2})

- Patients will complete pain assessment/compliance to treatment questionnaire.

Final Follow-up Assessment 3, Day 56 + t_{3_0} (-6 days to +6 days) (t_{3_3})

- Patients will complete pain assessment/compliance/satisfaction with treatment questionnaire.

6.7 *Withdrawal Visit*

- Record date and reason for withdrawal.
- Obtain pain assessment and treatment compliance/satisfaction information only if withdrawal occurs during an in-office visit, if consent was not withdrawn.

7 STUDY PROCEDURES/EVALUATIONS

7.1 *Study Procedures and Evaluations*

After entry into the study, a patient will undergo a baseline visit that will involve visual inspection of the oral cavity and further evaluation of the most sensitive tooth/teeth identified by the patient. Data regarding the duration and impact of symptoms, pain frequency and intensity, types and number of teeth affected, and DH treatment will be recorded.

Patients who return to the dental office within 8 weeks after the baseline visit due to continued discomfort on the tooth/teeth that received initial treatment and/or dentists' recommendation will be re-examined by the practitioner as described above. If the diagnosis has not changed, any second-line treatment for DH that is implemented and/or prescribed will be recorded. If patients return to the dental office within 8 weeks after the second-line treatment visit due to continued discomfort and/or dentists' recommendation, another re-examination will occur as described above, and any third-line treatment that may be implemented/and or prescribed will be recorded. The patient pain assessment is completed at the office visit after re-examination (see Subsection 7.2 below), and follow-up pain assessments via online or mailed questionnaire will occur through 8 weeks after the second/third-line treatment visit(s).

7.2 Questionnaire Administration

Prior to enrolling study patients, participating practitioners will complete an online practitioner questionnaire that will ascertain modalities used to diagnose DH as well as treatment modalities and approaches towards treatment of DH (see Section 3.2).

Practitioners will be asked about their patients' predisposing and enabling variables at/ or soon after the baseline visit (see Section 3.2.2).

At the baseline visit after the oral examination, patients will complete a pain assessment questionnaire that will ascertain the pain intensity, frequency, and duration. Patients will record pain levels by using LM pain scales that were developed at the University of Washington specifically to assess the pain associated with DH (Heaton et al., 2013). These four 100-millimeter (mm) horizontal scales are labeled with descriptive terms to assess the intensity, duration, tolerability and description of the participant's pain experience. Patients will also complete a standard 100-mm horizontal VAS on which the endpoints are marked "not painful" and "most intense pain sensation imaginable."

The clinical symptom of DH is likely associated with the "overall patient experience" because there is likely spatial summation. When an individual drinks cold fluids, for example, his/her DH/pain would be associated with multiple teeth (if multiple teeth are sensitive). Rating each tooth could only be achieved if the dentist systematically isolated each tooth and stimulated each one separately -- which doesn't mimic the clinical condition. The VAS/LM ratings will be applied to assess the overall patient pain experience associated with DH. The LM pain scales capture specific dimensions of pain that characterize the DH pain response (Heaton et al., 2013).

At 1-, 4- and 8- weeks post-baseline and/or second/third-line treatment visit(s), pain intensity, frequency, and duration will be re-ascertained as described above to measure patient-reported pain outcomes via an online or mailed questionnaire. Compliance with treatment will also be assessed via one Likert-like question. Treatment satisfaction will be assessed by one VAS question 8-weeks post the last treatment visit.

8 ASSESSMENT OF SAFETY

8.1 Specification of Safety Parameters

Safety monitoring for this study will focus on unanticipated problems involving risks to participants, including unanticipated problems that meet the definition of a serious adverse event (SAE).

8.1.1 *Unanticipated Problems*

The Office for Human Research Protections (OHRP) considers unanticipated problems involving risks to subjects or others to include, in general, any incident, experience, or outcome that meets **all** of the following criteria:

- Unexpected in terms of nature, severity, or frequency given (a) the research procedures that are described in the protocol-related documents, such as the IRB-approved research protocol and informed consent document; and (b) the characteristics of the subject population being studied;
- Related or possibly related to participation in the research (possibly related means there is a reasonable possibility that the incident, experience, or outcome may have been caused by the procedures involved in the research); and
- Suggests that the research places subjects or others at a greater risk of harm (including physical, psychological, economic, or social harm) than was previously known or recognized.

8.1.2 *Serious Adverse Events*

An SAE is one that meets one or more of the following criteria:

- Results in death
- Is life-threatening (places the subject at immediate risk of death from the event as it occurred)
- Results in inpatient hospitalization or prolongation of existing hospitalization
- Results in a persistent or significant disability or incapacity
- Results in a congenital anomaly or birth defect

An important medical event that may not result in death, be life threatening, or require hospitalization may be considered an SAE when, based upon appropriate medical judgment, the event may jeopardize the subject and may require medical or surgical intervention to prevent one of the outcomes listed in this definition.

8.2 Reporting Procedures

Incidents or events that meet the OHRP criteria for unanticipated problems require the creation and completion of an unanticipated problem report form. OHRP recommends that investigators include the following information when reporting an adverse event (AE), or any other incident, experience, or outcome as an unanticipated problem to the IRB:

- Appropriate identifying information for the research protocol, such as the title, investigator's name, and the IRB project number;
- A detailed description of the AE, incident, experience, or outcome;
- An explanation of the basis for determining that the AE, incident, experience, or outcome represents an unanticipated problem; and
- A description of any changes to the protocol or other corrective actions that have been taken or are proposed in response to the unanticipated problem.

To satisfy the requirement for prompt reporting, unanticipated problems will be reported using the following timeline:

- Unanticipated problems that are SAEs will be reported to the IRB and to NIDCR within 1 week of the investigator becoming aware of the event.
- Any other unanticipated problem will be reported to the IRB and to NIDCR within 2 weeks of the investigator becoming aware of the problem.
- All unanticipated problems should be reported to appropriate institutional officials (as required by an institution's written reporting procedures), the supporting agency head (or designee), and OHRP within 1 month of the IRB's receipt of the report of the problem from the investigator.

All unanticipated problems will be reported to NIDCR's centralized reporting system via Rho Product Safety:

- Product Safety Fax Line (US): [name]
- Product Safety Fax Line (International): [contact]
- Product Safety Email: [contact]

General questions about SAE reporting can be directed to the Rho Product Safety Help Line (available 8:00AM – 5:00PM Eastern Time):

- US: [name]
- International: [contact]

9 STUDY OVERSIGHT

In addition to the Grant PI's (GPI) and Study PI's (SPI) responsibility for oversight, study oversight will be under the direction of the PBRN Data and Safety Monitoring Board (DSMB) composed of members with expertise in dentistry, practice-based research, study design and statistics. The DSMB will meet at least annually to assess safety and efficacy data for the study. If safety concerns arise, more frequent meetings may be held. The DSMB will operate under the rules of an NIDCR-approved charter that will be approved at the organizational meeting of the DSMB. At this time, most data elements that the DSMB needs to assess will be clearly defined. The DSMB will provide recommendations to the NIDCR.

10 CLINICAL SITE MONITORING

Clinical site monitoring is conducted to ensure that the rights of human subjects are protected, that the study is implemented in accordance with the protocol and/or other operating procedures, and that the quality and integrity of study data and data collection methods are maintained. The network RAS will be responsible for clinical site monitoring for this study. RCs at each RAS will provide study training to practitioner sites and perform clinical site monitoring activities, to evaluate study processes and documentation based on NIDCR standards and principles of good clinical practice.

All details about clinical site monitoring will be documented in a Clinical Monitoring Plan (CMP) developed by Westat, under the direction of the National Dental PBRN, in collaboration with the NIDCR Office of Clinical Trials Operations and Management (OCTOM) and the NIDCR Program Official. The CMP will specify site training activities, the type and frequency of monitoring, monitoring procedures, the level of clinical site monitoring activities (e.g., the percentage of subject data to be reviewed), and the distribution of monitoring reports. Some monitoring activities may be performed remotely, while others will take place at each practitioner site. The RCs will provide reports of the findings from monitoring and associated action items in accordance with the details described in the CMP. Documentation of monitoring activities and findings will be provided to the practitioner, GPI, SPI, OCTOM, and the NIDCR. The NIDCR reserves the right to conduct independent audits as necessary.

11 STATISTICAL CONSIDERATIONS

The study is characterized by an estimation- rather than hypothesis-driven approach. The aims of identification and quantification of dentists' selected treatment(s) for DH and methods selected for the diagnosis of DH in the practice setting will be addressed by estimation of percentages of dentists using each method and percentages of patients for which each method was used, and calculation of confidence intervals (CIs) to evaluate the precision of each estimate.

11.1 Sample Size Considerations

The expected sample for the study will include approximately 180 practitioners, each enrolling 14 patients presenting with DH, for a total sample size of approximately 2,520 patients.

Calculations of sample size requirements for the primary objectives addressing estimation of percentages were based on widths of 95% confidence intervals for binomial proportions, adjusted for the effect of clustered sampling, with clusters defined by sampling multiple patients within the same dental practice. Adjustment for clustering was done by calculating effective sample sizes using variance inflation factors for a range of likely values of intracluster correlation (ICC). Power to detect a difference between proportions of dentists using each of the treatment modalities were estimated for chi-square tests, adjusted for the effect of clustered sampling in order to approximate the power of the proposed GEE analysis.

Sample size requirements for the primary objective of characterizing the trajectories of patient-reported pain outcomes over the study period, and for comparing these changes among the different treatments selected by the practitioners, were based on the expected widths of 95% CIs for the percentages of use of each of the treatments and diagnostic methods, and secondarily on t tests for comparisons of changes in VAS scores between two treatments, adjusted for the effect of clustering and for multiple treatment comparisons, again in order to approximate the power of the proposed GEE analysis. Power was calculated for comparison of two groups because the actual number of treatments observed will not be known until after the data is collected. In the absence of information on group size, the sample was assumed to be equally divided. Power was calculated for the conventional "medium effect size", represented by a between-group difference in means equal to one-half of the within-group standard deviation. Additionally, the difference in means that would be detectable with 80% power was calculated, and expressed as a multiple of the within-group standard deviation. Expected CI widths were based on the Normal approximation to the binomial distribution, and were calculated around 50% in order to provide conservative estimation. Precision of estimation of mean change in pain scores was calculated based on the widths of 95% CIs for change in reported pain scores, also using the expected mean numbers of subjects in equal-sized treatment groups. These CIs are expressed in standard deviation units.

The actual analysis will compare all the treatment groups that occur in the study, using an analysis of variance approach which will incorporate the entire sample. While the groups will be smaller than in this approximation, this will be somewhat offset by incorporating the entire sample in calculation of the standard error, so that power will be greater than would be calculated using only a portion of the patients in separate pairwise comparisons of treatment groups.

The nQuery Advisor version 7.0 software package was used to calculate expected confidence interval widths and power estimates.

Outcome measure used for calculations

The outcome measures that were used for sample size calculations for tabulation of treatment and diagnostic method use were the treatment techniques listed by the dentists and the diagnostic techniques, as presented in the dentist surveys. The sample size calculations for these are identical, but the number of treatment techniques is not known in advance, while we will know the number of diagnostic techniques that will be included. Patients' rating of DH using VAS responses were used as the outcome variable for evaluation of patient-reported pain outcomes over time.

Test statistic

Power for hypothesis testing was based on t tests and chi-square tests. Precision of estimation of percentages was based on widths of 95% confidence intervals for the binomial distribution. Precision of estimation of mean change in pain scores was based on widths of 95% confidence intervals for the normal distribution.

For the primary objective, study precision calculations were based on widths of 95% confidence intervals, rather than on power of hypothesis tests.

Type I error rate

The Type I error rate will be set at 5% for all analyses.

Type II error rate

The target Type II error rate is 20%, corresponding to statistical power equal to 80%. Power was calculated for a range of effect sizes, yielding ranges of power estimates.

Method for adjusting calculations for planned interim analyses, if any

No interim analyses are planned.

Assumptions used in calculations

[figure not shown]
Confidence interval width and power estimation for percentages of the dichotomous outcomes use of treatment modality and use of diagnostic techniques were based on

event rates of 50%, yielding the most conservative estimates by providing the widest estimated confidence interval width and a lower bound on power. This approach was used in order to somewhat offset possible inflation of power estimates due to approximation of equivalence of adjusted chi-square and t tests to the proposed GEE analysis, or to other errors of assumption in the calculations.

[figure not shown]
Data for objectives 1 and 2 are collected cross-sectionally, at a single patient visit. Thus, withdrawals are not anticipated for these analyses. For objective 3, loss to follow-up is a possibility. All available data for each patient will be used in the GEE analysis models. Least-squares adjusted means will be calculated in order to avoid biasing main effects means due to missing values.

Present calculations from a suitable range of assumptions to gauge the robustness of the proposed sample size. Most assumptions are not accurate as point estimates.

[figure not shown]
Effective sample sizes were calculated for 180 dentists, 10 to 20 patients per dentist, and values of ICC from 0.00 to 0.05. Expected widths of 95% confidence intervals around a true proportion of 0.50 were calculated for each effective sample size. The value of 0.50 was used as this is the value that yields the maximum variance for a binomial distribution, for a given sample size. Thus, these calculations provide upper bounds for the widths of confidence intervals for each sample size, providing conservative estimates in case ICC is higher than expected. Effective total sample sizes for the different values of ICC and numbers of patients per dentist are presented in the following chart.

[figure not shown]
The expected widths of confidence intervals for the primary estimation aims are presented in the following chart. The first set of expected widths was calculated for the entire sample, to illustrate the total information content of the sample, given each of the sample size choices. These expected widths range from 3.3%, reflecting estimation within $\pm 1.65\%$, for 20 patients per dentist and ICC equal to 0.0, to 5.0%, reflecting estimation within $\pm 2.5\%$, for 10 patients per dentist and ICC equal to 0.05. As seen in the plot, increasing the number of patients per dentist from 10 to roughly 16 provides substantial increases in precision, with smaller gains in precision with increases to 18 or 20 patients per dentist.

Assuming that four main treatment groups occur, then the expected widths of 95% CIs on the percentages of patients in each of these subgroups would range from 13.1% (estimation within $\pm 6.5\%$) for 20 patients per dentist and ICC equal to 0.0 to 22.3% (estimation within $\pm 11.15\%$) for 10 patients per dentist and ICC equal to 0.05. The expected widths of these CIs are shown in the following chart, which presents the same pattern across sample sizes as that for the entire sample.

[figure not shown]

Precision of estimation of mean change in reported pain scores is shown in the following chart. Four equal-sized subgroups of the total sample were assumed. Widths were calculated for CIs within a single subgroup. Precision is represented as the widths of 95% confidence intervals, based on the Normal distribution, in units of standard deviation of the change scores.

[figure not shown]

Power to detect a medium effect size for difference in VAS score between treatments is approximately 100% for all effective sample sizes that were considered. Differences between group means that would be detectable range from 0.095sd for 20 patients per dentist and ICC equal to 0.0 to 0.160sd for 10 patients per dentist and ICC equal to 0.05. Thus, all configurations that were considered provide substantial power to detect very small effect sizes, yielding confidence that the study will be adequately powered,

even if ICC is larger than those assumed in the power calculations. Power to detect a difference between treatment group means is shown in the following chart.

Given the results of these power calculations and practical considerations, we will recruit 180 dentists, who will each recruit 14 patients, for a total sample size of 2,520 patients. This will provide protection against loss of power due to potential dropout of patients or of dentists, and against finding larger than expected correlation among observations made by the same dentists. If a patient loss to follow-up of 20% were to occur, the study would still include 2,016 patients, which would still provide essentially 100% power to detect a medium effect size, for likely magnitudes of ICC. Similarly, while it is unlikely that practitioner dropout will occur, loss of as many as 10 practitioners would result in a total expected sample size of 2,380 patients, again providing very high power if ICC is of the expected magnitude. The proposed sample size provides substantial protection against the possibilities that ICC might be higher than anticipated or that the effect size might be smaller than anticipated.

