11.2 Final Analysis Plan

Analysis plan for Primary Objectives:

#1. To characterize methods of diagnosing DH in the practice setting.

(This will done by asking questions by means of an online questionnaire on what practitioners usually do when diagnosing DH.)

Practitioners' responses to questionnaire items will be summarized and reported as frequencies and percentages. Ninety five percent confidence intervals will be calculated for percentages. The primary analytic approach for this Aim will not be based on hypothesis testing.

#2. To characterize dentists' selected treatment(s) of DH.

Analysis approach: This descriptive aim will be addressed by tabulating the treatment modalities used by practitioners during the study. Percentages of practitioners using each modality and percentages of total patients who received each modality will be calculated. Confidence intervals for percentages of patients receiving each of the treatment modalities will be calculated, with adjustment for clustering by dentist. Comparisons of percentages among the treatment modalities will be conducted using a mixed model logistic regression, to account for the effect of correlation due to obtaining multiple observations from each practitioner. A term representing the individual practitioner will be specified as a random effect in the analytic model, and estimation will be implemented using GEE. An indicator variable representing treatment modality will be included as a fixed effect.

#3. To characterize patient-reported pain outcomes over time.

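### The confidence interval widths in Section 11.1 (3.3% to 5.0%) are patient-level; percentages of dentists rest on at most 180 units and have a width of about 14.6 points at 50%

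*Protocol*

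**What the plan says.** Section 11 describes an estimation study and names two kinds of percentage: "estimation of percentages of dentists using each method and percentages of patients for which each method was used", each with a confidence interval. Section 11.1 adds that precision for the primary objective rests on interval widths rather than on power.

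The calculation is in Section 11.1. Clusters are patients within a practice. "Effective sample sizes were calculated for 180 dentists, 10 to 20 patients per dentist, and values of ICC from 0.00 to 0.05". Each of these sizes was then converted to the width of a 95% interval, taking the true value as one half. The results are introduced so: "The expected widths of confidence intervals for the primary estimation aims are presented in the following chart". The whole-sample widths run from 3.3% (20 patients per dentist, ICC 0) to 5.0% (10 patients per dentist, ICC 0.05), and the text calls such widths upper bounds for each sample size.

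The same section takes its outcomes, treatment and diagnostic techniques, from the dentist surveys and continues: "The sample size calculations for these are identical, but the number of treatment techniques is not known in advance". On power it says: "Power to detect a difference between proportions of dentists using each of the treatment modalities were estimated for chi-square tests", with an adjustment for clustered sampling.

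Section 11.2 bases Primary Objective 1 on the online practitioner questionnaire: "Practitioners' responses to questionnaire items will be summarized and reported as frequencies and percentages", with 95% intervals. For Primary Objective 2 it plans percentages of practitioners and percentages of patients, with cluster-adjusted intervals for the latter. Sections 4 and 7.2 have dentists complete the questionnaire before they enrol patients.

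**The concern.** The unit counted in the calculation is the patient. For Objective 1 the unit of analysis is the dentist, who answers once and before any patient is enrolled. Neither the number of patients per dentist nor the correlation among patients of one dentist can enter the precision of such a percentage. The practitioner percentages in Objective 2 also have no more than one unit per dentist.

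Because interval width is the protocol's stated basis for the primary objective, a reader would expect diagnostic-method percentages to be estimated within about ±2.5 points at worst. The gain in precision that Section 11.1 describes when patients per dentist rise from 10 to about 16 would also be read as applying to them. The power statement has the same problem of unit: it speaks of proportions of dentists but adjusts for clustering, where the dentist is the cluster.

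**Working it through.** **Inputs, all from Section 11.1:** 180 dentists; 10 to 20 patients per dentist (m), 14 planned; ICC 0.00 to 0.05; a loss of 10 dentists considered. Method: "Expected CI widths were based on the Normal approximation to the binomial distribution, and were calculated around 50" percent.

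**Formulas**
- Effective number of patients: n_eff = 180m / (1 + (m − 1) × ICC)
- Full width of the 95% interval: 2 × 1.96 × √(p(1 − p)/n), which is 1.96/√n at p = 0.50

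**Step 1. Reproduce the stated patient-level range**

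| m | ICC | n_eff | Width at 50% | Protocol |
|---|---|---|---|---|
| 20 | 0 | 3,600 | 1.96/√3,600 = 3.27% | 3.3% |
| 10 | 0.05 | 1,800/1.45 = 1,241 | 1.96/√1,241 = 5.56% | 5.0% |
| 14 | 0 | 2,520 | 3.90% | not stated in the text |
| 14 | 0.05 | 2,520/1.65 = 1,527 | 5.02% | not stated in the text |

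The narrow end reproduces. The wide end does not for the configuration to which it is attached. A width of 5.0% needs an effective size of about 1,537, close to 14 patients per dentist at ICC 0.05 (1,527) or 10 per dentist at ICC 0.02 (1,525). Either way, the range can only come from counts of patients.

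**Step 2. Same method, dentist as the unit**

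| Dentists | True percentage | Full width | Half-width |
|---|---|---|---|
| 180 | 50% | 1.96/√180 = 14.6 points | ±7.3 |
| 170 | 50% | 1.96/√170 = 15.0 points | ±7.5 |
| 180 | 20% | 3.92 × √(0.16/180) = 11.7 points | ±5.8 |
| 180 | 10% | 3.92 × √(0.09/180) = 8.8 points | ±4.4 |

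The choice of interval matters little: at 180 dentists and 50%, the Clopper-Pearson width is 15.1 points and the Wilson width 14.5.

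**Step 3. Compare**
- 14.6/5.0 = 2.9 and 14.6/3.3 = 4.4.
- Widths of 5.0% and 3.3% would need about 1,537 and 3,528 independent dentists.
- At 10% use, 8.8 points still exceeds the whole stated range.

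**Step 4. Compare the stated data sources**
Section 11.1 says that data for objectives 1 and 2 are collected at one patient visit. Section 11.2 takes Objective 1 from the online questionnaire, which precedes enrolment. Both cannot describe the same Objective 1 data.

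**The case against.** The strongest reply is that the calculation does fit an estimand in the protocol. Section 11 lists percentages of patients for diagnosis as well as for treatment. Section 3.2.1 opens by saying that practitioner forms at patient visits also contribute. Section 11.2 plans cluster-adjusted intervals for patient percentages. Section 11.1 says the whole-sample widths show the information content of the sample, and nowhere expressly assigns 3.3% to 5.0% to percentages of dentists. This stands as far as it goes: patient-level widths belong in the section. But they are presented as the widths for the primary estimation aims without restriction, Section 11.2 analyses Objective 1 only from the questionnaire, and the text gives no figure for 180 dentists.

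Four stronger readings might be inferred and are not supported:
- *That the sentence on identical calculations is itself the error.* It compares treatment with diagnostic techniques, and at one common unit it is true. Its defect is that it does not name the unit.
- *That patients per dentist is irrelevant to every dentist-level percentage.* This is secure for questionnaire items. Objective 2 tabulates modalities used during the study, and whether a dentist is seen to use one can depend on how many patients are enrolled.
- *That power to compare modalities is overstated by a known amount.* The text gives no detectable difference for proportions, and a paired calculation would need discordance values that the protocol does not supply.
- *That the study is too small or its reported intervals will be wrong.* No target width is set, and Section 11.2 already plans intervals for practitioners' responses.

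**Conclusion.** The point holds as an error in the stated precision. For Objective 1 and the practitioner percentages in Objective 2, the widths in Section 11.1 use the wrong unit and are too narrow by a factor of about 2.9 against their own upper end. This rests on the protocol's convention (Normal approximation at 50%, the widest case), on all 180 dentists responding, and on no finite-population correction. The mismatch at the upper end, 5.6% against 5.0%, is a separate and smaller slip in the same sentence. The conclusion concerns what the protocol promises; it does not show that the planned enrolment is inadequate.

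**What to change.** In Section 11.1:
1. Label the chart and the whole-sample range as applying to percentages of patients only.
2. Correct the upper end to 5.6% for 10 patients per dentist and ICC 0.05, and give the range for the planned 14 per dentist: 3.9% (ICC 0) to 5.0% (ICC 0.05).
3. Add the widths for percentages of dentists: 14.6 points with 180 and 15.0 with 170, at 50%. State that for questionnaire items they do not depend on patients per dentist or ICC.
4. Keep the sentence on identical calculations, but say which unit it refers to.
5. Reconcile the statement that Objective 1 data come from a patient visit with the questionnaire source in Section 11.2.
6. In the power statement, either refer to proportions of patients, which is what a cluster-adjusted chi-square test addresses, or drop it for proportions of dentists.

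The cost is wording and a short recalculation, with no extra enrolment. The only downside is a less favourable stated precision.
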